#### 10.3.4 Additional Protocol-Specific Expedited Adverse Event Reporting Exclusions

For this protocol only, grade 3 laboratory AEs that do not meet criteria for DLT or result in a change study treatment do not require expedited reporting via CTEP-AERS. However, they still must be reported through the routine reporting mechanism (Section 10.4).

### 10.4 Routine Adverse Event Reporting

All Adverse Events **must** be reported in routine study data submissions. **AEs reported expeditiously through CTEP-AERS must also be reported in routine study data submissions.**

Adverse event data collection and reporting, which are required as part of every clinical trial, are done to ensure the safety of patients enrolled in the studies as well as those who will enroll in future studies using similar agents. AEs are reported in a routine manner at scheduled times during the trial using Medidata Rave. For this trial the Adverse Event CRF is used for routine AE reporting in Rave.

### 10.5 Pregnancy

Although not an adverse event in and of itself, pregnancy as well as its outcome must be documented via **CTEP-AERS**. In addition, the **Pregnancy Information Form** included within the NCI Guidelines for Adverse Event Reporting Requirements must be completed and submitted to CTEP. Any pregnancy occurring in a patient or patient's partner from the time of consent to 150 days (5 months) after the last dose of study treatment must be reported and then followed for outcome. Newborn infants should be followed until 30 days old. Please see the "NCI Guidelines for Investigators: Adverse Event Reporting Requirements for DCTD (CTEP

and CIP) and DCP INDs and IDEs” (at [http://ctep.cancer.gov/protocolDevelopment/adverse\\_effects.htm](http://ctep.cancer.gov/protocolDevelopment/adverse_effects.htm)) for more details on how to report pregnancy and its outcome to CTEP.

## 10.6 Secondary Malignancy

A *secondary malignancy* is a cancer caused by treatment for a previous malignancy (*e.g.*, treatment with investigational agent/intervention, radiation or chemotherapy). A secondary malignancy is not considered a metastasis of the initial neoplasm.

CTEP requires all secondary malignancies that occur following treatment with an agent under an NCI IND/IDE be reported expeditiously via CTEP-AERS. Three options are available to describe the event:

- Leukemia secondary to oncology chemotherapy (*e.g.*, acute myelocytic leukemia [AML])
- Myelodysplastic syndrome (MDS)
- Treatment-related secondary malignancy

Any malignancy possibly related to cancer treatment (including AML/MDS) should also be reported via the routine reporting mechanisms outlined in each protocol.

## 10.7 Second Malignancy

A second malignancy is one unrelated to the treatment of a prior malignancy (and is **NOT** a metastasis from the initial malignancy). Second malignancies require **ONLY** routine AE reporting unless otherwise specified.

## 11. STUDY CALENDAR

Baseline evaluations (i.e. physical exam, vital signs, weight, performance status, laboratory tests, including pregnancy test, EKG (as indicated)) are to be conducted within 2 weeks prior to study registration. Radiologic evaluations must be done  $\leq 4$  weeks prior to study registration. In the event that the patient's condition is deteriorating, the physical exam and laboratory evaluations should be repeated within 48 hours prior to initiation of the next cycle of therapy. All in-clinic treatments and assessments can be carried out  $\pm 2$  days of the time points indicated below during induction to allow for holidays, inclement weather, and other unexpected conflicts. In the maintenance phase, a window of  $\pm 3$  days is allowed for Day 1 of each cycle.

	Induction (Cycles 1-4)							Maintenance (Cycles 5-17) D1	End of study treatment (at least 30 days after last entinostat dose)	Follow-up a
	Pre- Study	C1 D1	C1 D8	C1 D15	C2D1	C3D1	C4D1			
Entinostat		A	A	A	A	A	A	A		
Atezolizumab		B			B	B	B	B	B j	B j
Carboplatin, Etoposide		C			C	C	C			
Informed consent	X									
Demographics	X									
Medical history	X									
Concurrent meds	X	X	X	X	X	X	X	X	X	
Physical exam	X	X	X	X	X	X	X	X	X	
Vital signs	X	X	X	X	X	X	X	X	X	
Height	X									
Weight	X	X			X	X	X	X	X	
Performance status	X									
CBC w/diff, plts	X	X	X	X	X	X	X	X	X	
Comprehensive Chemistry Panel b	X	X	X	X	X	X	X	X	X	
PT/INR	x									

NCI Protocol #: 10399  
 Version Date: August 17, 2021

	Induction (Cycles 1-4)							Maintenance (Cycles 5-17) D1	End of study treatment (at least 30 days after last entinostat dose)	Follow-up a
	Pre-Study	C1 D1	C1 D8	C1 D15	C2D1	C3D1	C4D1			
TSH, T3, T4 n	X	X			X		X	X i	X i	
EKG (as indicated)	X									
Adverse event evaluation		X	X	X	X	X	X	X	X	
Tumor measurements (RECIST assessments)	X					X		X e	X f	X f
Radiologic evaluation	X g					X g		X g	X g	X g
Overall Survival b										X
Pregnancy test c	X									
Archival tumor submission	X									
Tumor biopsy d	X									X k
Blood in cfDNA Streck tube for ctDNA		X								X k
Flow cytometry, ELISPOT		X			X	X	X			X k
Entinostat PK l		X	X	X	X					
Atezolizumab PK m		X			X	X	X	X		

A: Entinostat: Dose as assigned; Days 1, 8, and 15 of each cycle  
 B: Atezolizumab: Dose as assigned; Day 1 of each cycle  
 C: Carboplatin, etoposide: Dose as assigned; Carboplatin Day 1, Etoposide Days 1-3, cycles 1-4. For patients that cannot tolerate carboplatin and etoposide, discontinue induction cycles and follow the Maintenance regimen.  
 a: Follow-up assessments will be conducted for up to 5 years from the date of registration. Patients that discontinue study treatment for reasons other than disease progression will follow the imaging schedule per footnotes f and g. Patients that discontinue study treatment for disease progression will be followed every 3 months for the first 2 years and then every 6 months for years 3-5 from the date of registration.  
 b: Albumin, alkaline phosphatase, total bilirubin, bicarbonate, BUN, calcium, chloride, creatinine, glucose, LDH, phosphorus, potassium, total protein, SGOT [AST], SGPT [ALT], sodium.  
 c: Pregnancy test for women of childbearing potential.  
 d: Tissue biopsy is not required at screening if archival tissue is available. Tissue biopsy at progression (off study) is optional. PT/INR may be required per institutional requirements for biopsies.

NCI Protocol #: 10399

Version Date: August 17, 2021

	Induction (Cycles 1-4)							Maintenance (Cycles 5-17) D1	End of study treatment (at least 30 days after last entinostat dose)	Follow-up a
	Pre- Study	C1 D1	C1 D8	C1 D15	C2D1	C3D1	C4D1			

e: Tumor measurements are repeated every 6 weeks (+/- 1 week) for year 1.
 
f: Tumor measurements are repeated every 3 months (+/- 2 weeks) for year 2, then every 6 months (+/- 1 month) thereafter. Documentation (radiologic) must be provided for patients removed from study for progressive disease.
 
g: CT Chest/Abd/Pelvis are performed within 4 weeks of study registration and then every 6 weeks(+/- 1 week) for year 1, every 3 months (+/- 2 weeks) for year 2, then every 6 months (+/- 1 month) thereafter until progression. Patients who discontinue study treatment for reasons other than disease progression will continue radiographic evaluations per this schedule during Follow-Up until disease progression is documented. For pts with untreated brain mets, brain MRI is performed within 4 weeks of study enrollment and then subsequently at same schedule as CT imaging; otherwise as clinically indicated.
 
h: If participant is no longer coming to the study site, study staff will call or email the participant to check overall survival every 3 months for years 1-2, then every 6 months (+/- 1 month) until 5 years from registration.
 
i: Day 1 of every even cycle.
 
j: May continue per investigator/patient discretion as standard of care. Labs, vitals, performance status should be done as routine standard of care and are not indicated on this table. End of treatment visit may occur on a day when standard of care atezolizumab is administered or a separate day.
 
k: Tumor biopsy (optional), blood collection in cfDNA Streck tube for ctDNA, Flow cytometry, and ELispot are to be performed at the time of progression. Refer to Sections 5.1 and 5.5.
 
l: Entinostat PK on Cycles 1-2, Day 1: prior to entinostat, ~0.5 hr post dose, and ~2 hrs post dose; Cycles 1-2, Day 2: prior to etoposide infusion; Cycle 1, Day 8 and 15: prior to entinostat.
 
m: Atezolizumab PK on Day 1 of Cycles 1 and 2: prior to atezolizumab and after the end of the atezolizumab infusion at the same time as the ~2 hr post entinostat PK. On Day 1 of Cycles 3, 4, 6, and 8: prior to atezolizumab and ~0.5 hr after completion of atezolizumab infusion.
 
n: Free or total T3/T4 may be performed per institutional standards.
										

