## SCHEMA

[figure not shown]

Figure 1: Study Schema

Dose Escalation Schedule								
Dose Level	Induction (Cycles 1-4)				Maintenance (Cycles 5-17)		Cycle Length	
	Dose				Dose			
	Carboplatin	Etoposide	Atezolizumab	Entinostat	Atezolizumab	Entinostat		
Level -1 (ME)	AUC 5 IV D1	100 mg/m  IV D1-3	1200 mg IV D1	None	1200 mg IV D1	5 mg PO D1, 8, 15	21 days	
Level 1*	AUC 5 IV D1	100 mg/m  IV D1-3	1200 mg IV D1	2 mg PO D1, 8, 15	1200 mg IV D1	5 mg PO D1, 8, 15	21 days	
Level 2	AUC 5 IV D1	100 mg/m  IV D1-3	1200 mg IV D1	3 mg PO D1, 8, 15	1200 mg IV D1	5 mg PO D1, 8, 15	21 days	
Level 3	AUC 5 IV D1	100 mg/m  IV D1-3	1200 mg IV D1	5 mg PO D1, 8, 15	1200 mg IV D1	5 mg PO D1, 8, 15	21 days	

\*Starting Dose Level.  
 IV = intravenous, AUC = Area Under Curve, PO = Orally, ME = Maintenance entinostat.

Patients will receive up to 4 cycles of induction followed by maintenance treatment for a maximum of 1 year of combined treatment (or a total of 17 cycles). *Patients who are unable to tolerate carboplatin and etoposide, may discontinue induction and receive the maintenance regimen. If this occurs, maintenance may begin prior to Cycle 5 and can continue for a total of 1 year of treatment.*

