
For archival tissue, a copy of the corresponding anatomic pathology report, labeled with the patient study ID and Universal ID, must be sent with the tissue and uploaded to Rave. If submitting slides, then slides must be processed in order, and numbered sequentially.
 
 For new biopsies, a fine needle aspirate (FNA) should be obtained for diagnostic purposes and submitted to pathology. Cores should be obtained for research and not submitted to pathology for review. The Tissue Biopsy Verification Form (Appendix E), a copy of the radiology and/or operative reports from the tissue removal procedure and the diagnostic anatomic pathology report must be sent with the tissue to the EET Biobank. All reports must be labeled with the patient study ID and Universal ID.
 
 For any PK sample, the PK samples are on the days of drug administration. If drug administration is shifted due to a holiday or inclement weather, the PK should be collected on that day (and not the exact day listed above).
 
 If etoposide is held for any reason, the accompanying entinostat PK sample should not be collected.
		

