#### 5.7.2 Shipping of Blood Samples to JHU APC

##### 5.7.2.1 Specimen Shipping

- Specimens should be stored through the end of Cycle 2 and shipped as a batch by participant (more than one participant/shipment is acceptable).
- A participant's samples should be shipped to the JHU APC lab within 2 weeks of the last sample's collection date. (i.e., if C2D2 sample is collected on 9/1/2021, all of that participant's samples should be at the JHU APC lab by 9/15/2021).
- The JHU APC lab may contact the study team to request shipment off-schedule.
- **Please ship only 1 aliquot to the JHU APC laboratory within each shipment. Once receipt is confirmed, the back-up aliquot(s) may also be shipped. The back-up aliquots can be shipped at a later date with subsequent batches of samples for other participants.**

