6	Atezolizumab	ELISA CLIA: N GLP: Y	Integrated Pharmacokinetic profile of atezolizumab	Serum from Red top Tubes	C1D1 pre-dose and after the end of the atezolizumab infusion at the same time as the ~2 hours post entinostat PK; C2D1 pre-dose and after the end of the atezolizumab infusion at the same time as the ~2 hours post entinostat PK; C3D1 pre-dose and approximately 0.5 hours after the end of atezolizumab administration; C4D1 pre-dose and approximately 0.5 hours after the end of atezolizumab administration; C6D1 pre-dose and approximately 0.5 hours after the end of atezolizumab administration; C8D1 pre-dose and approximately 0.5 hours after the end of atezolizumab administration;	M	Pharmacoanalytical Shared Resource (PhASR), Ohio State University Comprehensive Cancer Center  [name].  [contact]

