### 7.2.2 Dose reductions for entinostat during maintenance

Regardless of dose level assignment at the start of the trial, 5 mg PO weekly will be the starting dose in the maintenance phase for all patients who did not require entinostat dose reductions

during induction. If entinostat is reduced or discontinued during the induction phase of the trial due to hematologic adverse events, entinostat will be resumed at the maintenance dose of 5 mg PO weekly as long as the adverse event(s) that led to discontinuation of entinostat have improved to grade  $\leq 1$ ; otherwise resume at the same dose as the end of the induction phase. If entinostat was reduced due to non-hematologic adverse events during induction, it will be continued at the same dose level in maintenance. If entinostat was discontinued due to non-hematologic adverse events in the induction phase, it will not be restarted in the maintenance phase.

Dose Level	Entinostat Dose
Starting Dose Level*	5 mg, PO weekly
1 st Dose Reduction	3 mg, PO weekly
2 nd Dose Reduction	2 mg, PO weekly
3 rd Dose Reduction	Discontinue entinostat
* Starting dose level of entinostat for maintenance cycles is 5 mg, PO weekly, irrespective of assigned dose level during induction cycles. PO = orally	

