### 9.3 Analysis of Secondary Endpoints

Adverse events and DLTs will be summarized by frequency and magnitude. The rate of feasibility of administering entinostat concomitantly with atezolizumab, carboplatin, and etoposide as determined by the proportion of participants who receive 3 or more cycles of the combination, will be calculated with a 90% confidence interval. The Kaplan Meier estimator will be used to estimate survival curves for all time to event endpoints including progression free survival (PFS) and overall survival (OS). The 9 month PFS rate will be estimated with a 90% confidence interval. Anti-tumor endpoints, including measures of tumor response and symptom relief, will be summarized using descriptive statistics. Tumor response will be measured using RESIST 1.1 criteria and reported as overall response rate (ORR) with a 95% confidence interval. Entinostat exposure will be determined for each patient using mixed effects pharmacokinetic modeling. Atezolizumab clearance, including a time-varying rate of change, will be determined for each patient using mixed effects pharmacokinetic modeling. Exposure-response assessments will be assess associations between entinostat exposure with the clinically significant toxicity, PFS and OS. Clearance-response will be assessed between baseline or time-varying atezolizumab clearance with the presence of cachexia, PFS and OS. Biomarker evaluations from exploratory objectives will be summarized using descriptive statistics.

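### Level -1 patients have no scheduled entinostat sample while on the drug, so the per-patient exposure promised in Section 9.3 cannot be obtained at that dose level

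*Combined protocol and SAP*

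**What the plan says.** **Sampling.** Section 11, footnote l, sets the entinostat draws as "Entinostat PK on Cycles 1-2, Day 1: prior to entinostat, ~0.5 hr post dose, and ~2 hrs post dose" and "Cycles 1-2, Day 2: prior to etoposide infusion; Cycle 1, Day 8 and 15: prior to entinostat". Sections 5.1 and 5.8 list the same times and mark them mandatory. Section 5.7.2.1 confirms that collection ends there: "Specimens should be stored through the end of Cycle 2 and shipped as a batch by participant". Footnote 3 to Section 5.1 adds: "For any PK sample, the PK samples are on the days of drug administration".

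**Dosing.** In the dose tables of the Schema and Section 6.1, Level -1 carries the tag ME ("ME = Maintenance entinostat"). It has no entinostat in Cycles 1-4 and 5 mg weekly from Cycle 5. Section 7.2.2 puts all levels on the same footing in maintenance: "Starting dose level of entinostat for maintenance cycles is 5 mg, PO weekly, irrespective of assigned dose level during induction cycles". Section 6.1 lets a patient who cannot tolerate the chemotherapy enter maintenance before Cycle 5.

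**Analysis.** Section 9.3 states: "Entinostat exposure will be determined for each patient using mixed effects pharmacokinetic modeling". It then relates exposure to toxicity, PFS and OS (exploratory objective 1.3.5). It makes no exception for Level -1 and names neither the exposure metric nor the period.

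**Atezolizumab timing.** The Section 5.8 row reads "C1D1 pre-dose and after the end of the atezolizumab infusion at the same time as the ~2 hours post entinostat PK", and C2D1 is handled the same way. In Cycles 3, 4, 6 and 8 the post-infusion sample is instead taken about 0.5 hours after the end of infusion.

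**The concern.** The sampling schedule follows the calendar of a patient who takes entinostat from Cycle 1. Level -1 is defined by not doing so. Its sampling window closes at C2D2, well before its first planned dose at C5D1. Either the tubes are drawn off drug or, if footnote 3 of Section 5.1 is applied, none are drawn. Both ways there is nothing from which to estimate that patient's clearance.

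The stake is objective 1.3.5 at that level. Level -1 is a real landing place for the design, and if it is selected as the MTD, the trial would report a chosen regimen with no scheduled entinostat concentrations behind it. The missing time anchor for the first two post-infusion atezolizumab samples also touches objective 1.3.6, which uses first-dose (baseline) atezolizumab clearance.

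**Working it through.** **1. Samples.** C1D1 (3) + C1D2 (1) + C1D8 (1) + C1D15 (1) + C2D1 (3) + C2D2 (1) = 10, of which 9 follow the first dose at Levels 1-3. None is scheduled in Cycles 3-17.

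**2. Planned dose against the sampling window** (17 cycles, 3 doses per cycle, no holds or reductions):

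| Level | Planned total, mg | In Cycles 1-2, mg | Maintenance share |
|---|---|---|---|
| -1 | 39 × 5 = 195 | 0 | 100% |
| 1 | 12 × 2 + 195 = 219 | 12 (5.5%) | 89% |
| 2 | 12 × 3 + 195 = 231 | 18 (7.8%) | 84% |
| 3 | 12 × 5 + 195 = 255 | 30 (11.8%) | 76% |

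**3. How many patients.** The plan's own figures were reproduced first. BOIN with target 0.20 and the default 0.6 and 1.4 multipliers gives boundaries 0.157 and 0.238. With elimination at posterior probability above 0.95, all 36 cells of the escalation table match. Simulating 6,000 trials per scenario under the Section 9.1.1 stopping rule gives Level -1 shares of 5.4, 10.6, 26.4 and 40.5% and mean sizes of 23.7, 23.8, 22.1 and 19.5, in line with Section 9.1.3. From the stated table:

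| Scenario | Treated at Level -1 | Mean N | Patients at Level -1 | Level -1 selected |
|---|---|---|---|---|
| 1 | 5.6% | 23.7 | 0.056 × 23.7 = 1.3 | 2.89% |
| 2 | 10.6% | 23.7 | 0.106 × 23.7 = 2.5 | 7.41% |
| 3 | 25.7% | 22.3 | 0.257 × 22.3 = 5.7 | 29.55% |
| 4 | 41.3% | 19.4 | 0.413 × 19.4 = 8.0 | 51.73% |

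These means include trials that never use Level -1. In the simulation 22.8, 34.5, 61.0 and 78.9% of trials treat someone there. Within those trials the mean is 1.29/0.228 = 5.7, 2.52/0.345 = 7.3, 5.83/0.610 = 9.6 and 7.91/0.789 = 10.0 patients.

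**4. What the model can recover.**
- *Levels 1-3.* The fraction of steady state reached by C2D1 is 1 − 2^(−504/t½). For the half-lives in Section 2.2.1.4 (54, 140 and 161 h) it is 99.8, 91.8 and 88.6%. A first-order Bayesian calculation used the nine post-dose samples and a one-compartment oral model. Its assumptions were a between-patient SD of 0.3-0.5 for log clearance and log volume, 0.8 for log absorption rate, and residual error of 20-40%. The documents give none of these. The posterior variance of a patient's log clearance falls to 2.5-33% of its prior variance, so individual clearance is estimable.
- *Level -1.* With no on-drug observation, posterior variance equals prior variance. The model can only return the population-typical value, not that patient's exposure.

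**5. Does Cycle 1-2 exposure misstate later exposure?** Only if it is used raw. The Level 1 to Level 3 dose ratio is 2/5 = 0.40 in Cycles 1-2. Over 39 weekly doses (about 9 months, no holds) it is (12 × 2 + 27 × 5)/(12 × 5 + 27 × 5) = 159/195 = 0.82.

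**6. Atezolizumab.** At Level -1 there is no entinostat dose on C1D1 or C2D1, so a time 2 hours after it is undefined. What remains is that the sample follows the end of infusion.

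**The case against.** Most of the defence stands, and it limits the point to Level -1.

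- A reader might infer that the 5 mg dose is never sampled. Level 3 takes 5 mg in induction and gives all ten samples on it. What goes unsampled is the scheduled maintenance phase.
- A reader might infer that exposure cannot be derived at Levels 1-3. Step 4 shows otherwise: early clearance plus the dosing record (the Appendix F diary) gives a predicted exposure. This does assume constant, dose-linear clearance. Linearity is stated from 2 mg/m² upward. At an assumed body surface area of 1.5-2.2 m², 2 mg is 0.9-1.3 mg/m² and 3 mg is 1.4-2.0 mg/m², at or below that floor. The prediction is therefore unverified in maintenance, but it is not impossible.
- A reader might infer a biased PFS/OS slope. Section 9.3 does not say that raw Cycle 1-2 exposure will be used, so step 5 is a warning about one possible metric and not a fault in a stated analysis. The 0.82 is also a best case without holds, reductions or early progression.
- A reader might suspect that stopping chemotherapy changes entinostat exposure. The documents report no such effect. Their stated hypothesis concerns atezolizumab, which is given in both phases.
- At Level -1, exposure in Cycle 1 is zero by design and needs no sample. Patients who never reach maintenance also have a known exposure of zero. An early switch could put C2D1 on drug; the C2D2 draw would then be dropped, because etoposide is not given. The counts in step 3 are therefore upper figures for those affected.
- The early atezolizumab sample is not untimed. It must follow the infusion, and Section 5.5.3.4.1 puts the exact collection time on the label. Only the nominal offset is lost.

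None of this supplies an on-drug concentration for a Level -1 patient who follows the planned course.

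**Conclusion.** The point holds for Level -1. On the planned course these patients have 0 of 39 planned entinostat doses within the sampling window, and Section 9.3 cannot deliver an individual exposure for them. On the plan's own operating characteristics this concerns on average 1.3 to 8.0 patients per trial, at a level selected in 2.89% to 51.73% of simulated trials. The lost nominal time for two atezolizumab samples is a smaller fault with the same cause.

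For Levels 1-3 the gap is verification only: maintenance is 76-89% of planned dose and no scheduled sample checks it. That conclusion rests on the assumed variability in step 4 and on clearance staying constant.

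Objective 1.3.5 is exploratory, and no escalation, elimination or MTD rule uses PK, so dose finding is unaffected. The change is worth making because it is cheap and because, without it, the objective cannot be answered at a level that the trial may select.

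**What to change.** 1. **Level -1 entinostat draws** (Sections 5.1 and 5.8, footnote l, and the shipping text in 5.7.2). Replace the Cycle 1-2 draws with sparse draws at existing Day 1 maintenance visits, starting from that patient's first entinostat dose. One example is C5D1 at about 0.5 and 2 hours; C6D1 pre-dose and at about 0.5 and 2 hours; and C7D1 pre-dose. That is 2 + 3 + 1 = 6 samples instead of 10.
2. **Level -1 atezolizumab timing** (Sections 5.1 and 5.8, footnote m). Take the C1D1 and C2D1 post-infusion samples about 0.5 hours after the end of infusion, as in Cycles 3-8.
3. **Section 9.3.** Relate Cycle 1 toxicity to Cycle 1 exposure. Relate PFS and OS to exposure predicted over time from individual clearance and actual dosing, not to Cycle 1-2 exposure. If item 1 is not adopted, restrict the entinostat exposure analysis to Levels 1-3 and say so.
4. **Optional, Levels 1-3.** Add one 4 mL pre-dose entinostat tube at C6D1 and C8D1, where atezolizumab PK is already drawn, to verify maintenance exposure.

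**Cost.** Text edits, no new visits and fewer tubes at Level -1. The Level -1 shipping batch closes later (after C7D1 in the example), and the 2-hour draws may lengthen two maintenance visits. Item 4 adds two small tubes per patient. Item 3 alone costs nothing but leaves Level -1 without entinostat PK.
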